One such format that has been widely adopted is the *self-guided* online intervention, where participants have access to the content on their own with minimal guidance provided. Previously, we utilized this medium to deliver a positive emotion intervention for individuals with elevated depression symptomatology. But while such interventions reduce barriers for participation, they are beset by high rates of attrition and poor adherence. Parallel research on other self-guided resources, namely Massive Open Online Courses (MOOCs), have found that the construct of *social presence* – or the ability to perceive others in an online environment – can enhance retention and engagement. Social presence may include features like providing welcome messages, displaying participant profiles, and facilitating online discussion amongst participants. Hence, eHealth and mHealth interventions are likely to benefit from the application of these social features.

With these considerations in mind, such social features may be particularly beneficial for caregiver participants; who experience higher levels of social isolation and loneliness compared to their peers. Hence, the objective of this proposal is to adapt the existing positive emotion intervention for SAGE LEAF – a socially enhanced, online intervention for Alzheimer's caregivers. If successful, SAGE LEAF may be scaled as an online resource that caregivers could utilize to better cope with the stressors of caregiving.

For the **1**) **user test**, we will be evaluating the SAGE LEAF platform's usability and usefulness. Non-Alzheimer's dementia caregivers recruited from the Northwestern Cognitive Neurology and Alzheimer's Disease Center (CNADC) (N=20) will participate in an extended user test where they will receive full access to the SAGE LEAF intervention, and provide their feedback through surveys and interviews on the platform's usability and usefulness upon conclusion of the 6-week program. Subsequently, the necessary refinements to the platform will be made based on the feedback received.

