Next, we will conduct a (N=30) single-arm pre-post 2) **pilot test / feasibility study** of SAGE LEAF for AD caregivers. Participants will receive access to the SAGE LEAF platform and complete the positive emotion skills intervention over 6 weeks. We will evaluate the number and percentage of participants retained at the post assessment as well as the means and ranges for the proportion of intervention content completed (i.e., number of pages viewed out of the total possible pages across all skills and lessons in the intervention) and participants' acceptability ratings (i.e., participants' ratings of whether they would recommend SAGE LEAF to other AD caregivers).

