#### 3.0 Sample Size:

We will recruit a total of 50 participants: 1) 20 participants for the user test and 2) 30 participants for the pilot test. These sample sizes are commensurate with the exploratory nature of this preliminary research.

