## **11.0** Consent Process:

For both phases, online consent will take place through a REDCap electronic consent form. Consent will be time-stamped and participants will be able to save, download, and/or print a copy of the consent form for their records. Participants will consent electronically by entering the date and by typing their full name into the form, which will represent their electronic signature. Participants will be considered "consented" only if they provide both items (date and electronic signature). Participants may also email the project director to request a copy of the consent form at any time.

If a participant chooses to withdraw during the study, their data will be retained up until their point of withdrawal. When a participant withdraws, they will no longer receive future assessments and they will no longer receive daily reminders to log-in to the website. Participants can consent to be contacted for future studies. They can also consent to receive SMS text messages to receive their survey assessments. Please refer to the consent form. Study staff will monitor the REDCap project daily in order to track any new completed consent documents and update study tracker.

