#### Withdrawal of participants

If a participant wishes to withdraw, he/she can communicate this on the phone or via email to the project director. Study staff will also be monitoring communications and potentially withdrawal requests coming through on the study website or study email. The participant will then be promptly withdrawn from the study, their data collected and eventually analyzed only up until the point of withdrawal. No further data will be collected after a participant has been withdrawn. We will document the reason for withdrawing.

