## 22.0 Statistical Analysis:

Statistical Analyses

We will calculate the medians and interquartile range (IQR) for primary measures that assessed the (1) usability, (2) usefulness, (3) feasibility, and (4) acceptability of the SAGE LEAF platform. In addition, we will calculate supplementary user metrics based on data collected by the platform (e.g., percentage of home practice activities completed and percentage of videos watched) that reflect various aspects of engagement. We calculated the means and SDs for the Social Presence Scale and applied them as a correlate with measures of usability, usefulness, feasibility, and acceptability. For measures related to preliminary outcomes, we will perform paired, 1-tailed t tests on the data collected during the baseline and postintervention assessments to examine changes in means. Analyses will be conducted using Excel (Microsoft Corporation) and R Studio (Posit).

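### The paired t tests use completers only; if dropout depends on the T1 score the mean change is biased, and a repeated-measures model on everyone with a T1 value avoids this at modest cost

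*Combined protocol and SAP*

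**What the plan says.** Section 22.0 (Statistical Analysis) specifies "paired, 1-tailed t tests on the data collected during the baseline and postintervention assessments" for the preliminary outcomes. It states no analysis set, missing-data assumption, alpha level or sensitivity analysis. Its primary measures are usability, usefulness, feasibility and acceptability, which are summarised by medians and interquartile ranges.

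The pilot in Section 1.0 is a "single-arm pre-post" study. Section 3.0 plans "1) 20 participants for the user test and 2) 30 participants for the pilot test" and justifies the numbers only by the exploratory purpose: "These sample sizes are commensurate with the exploratory nature of this preliminary research". The Phase 2 measures in Section 8.0 have two questionnaire time points, T1 and T2, so no intermediate score can stand in for a missing T2.

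On attrition, Section 1.0 says of self-guided online interventions in general that "they are beset by high rates of attrition and poor adherence". It adds that social presence may improve retention, and it makes retention at the post assessment an outcome. It forecasts no rate for this trial.

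On withdrawal, Section 11.0 says that "their data will be retained up until their point of withdrawal", and Section 17.0 (Withdrawal of participants) has "their data collected and eventually analyzed only up until the point of withdrawal". Section 19.0 has staff track missing assessments but gives no analysis method for them.

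**The concern.** A participant with T1 but no T2 contributes nothing to a paired t test. Change is usually related to the starting score: people who start high tend to come down and people who start low tend to come up. If leavers differ from stayers at T1, the stayers are a selected group whose mean moves for that reason alone. A randomised comparison might cancel part of this, but a single arm cannot.

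Take a scale on which higher is worse. If less burdened caregivers leave, completers appear to improve when nothing has changed. If more burdened caregivers leave, a real improvement is partly hidden. Because the test is one-tailed, the first case inflates false positives and the second makes the test conservative. The pilot's preliminary signal on burden, stress, depression and anxiety could then partly reflect who stayed. The T1 scores needed to correct this will already have been collected.

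**Working it through.** **Inputs from the documents.** N=30, one arm, two assessments, paired one-tailed t test. The plan has no power, effect-size, SD or dropout figure to reproduce.

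**Assumed inputs.** One-sided alpha 5%; SD 1 at both visits; T1-T2 correlation 0.5 to 0.7 for the main range (0.4 to 0.8 where stated); dropout 30% to 40% for the main range (up to 50% where stated). Dropout follows a logistic function of T1, with odds ratio per T1 SD of 1.6 (mild), 2.7 (moderate) or 7.4 (strong).

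**Bias of the completers' mean change.** Let b be the slope of T2 on T1. Then

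bias = (b - 1) x (mean T1 of completers - mean T1 of all).

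With equal SDs, b equals the correlation r. With dropout fraction f and a T1 difference D between stayers and leavers, the size is (1 - r) x f x D.

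| r | f | D (SD) | Formula | Simulated bias | One-sided 5% test, no true change, less burdened leave |
|---|---|---|---|---|---|
| 0.5 | 0.30 | 0.48 | 0.5 x 0.30 x 0.48 = 0.072 | 0.069 | 8.8% |
| 0.5 | 0.30 | 0.84 | 0.5 x 0.30 x 0.84 = 0.126 | 0.127 | 14% |
| 0.5 | 0.40 | 0.83 | 0.5 x 0.40 x 0.83 = 0.166 | 0.167 | 17% |
| 0.7 | 0.30 | 0.48 | 0.3 x 0.30 x 0.48 = 0.043 | 0.04 | 8% |
| 0.7 | 0.30 | 0.84 | 0.3 x 0.30 x 0.84 = 0.076 | 0.08 | 11% |

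For scale only, Section 1.0 gives a depression effect of d = -0.25 against control in the facilitator-delivered LEAF trial.

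**Model using all T1 values.** With an unstructured 2x2 covariance, the maximum-likelihood change is

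completers' change + (b - 1) x (mean T1 of all - mean T1 of completers),

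so the bias term is subtracted out. Results at r = 0.6, 30% dropout and odds ratio 2.7, with no true change:

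| | Paired t | Model |
|---|---|---|
| Bias (SD) | 0.10 | 0.00 |
| Standard error | 0.194 | 0.201 |
| Root mean squared error | 0.219 | 0.201 |
| 95% CI coverage | about 92% | about 96% |
| Rejection, low scorers leave | 12.8% | 5.0% |
| Rejection, high scorers leave | 1.7% | 4.2% |

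**Cost in precision (model SE / paired SE, r from 0.4 to 0.8).** At 30% dropout the ratio is 0.97 to 1.01 for a mild link, 1.02 to 1.04 for a moderate link and 1.10 to 1.13 for a strong link. At 40% dropout and r = 0.8 it is 1.02 (mild) and 1.08 (moderate). At 50% dropout with a strong link it is 1.29 to 1.34.

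**Limits.**
- If b = 1, the paired test has no bias even when dropout depends on T1, and the model costs about 6% in SE (30% dropout, moderate link).
- If dropout also depends on the unseen T2, the model is biased. At r = 0.6, 30% dropout and odds ratio 2.7 per SD of both T1 and the T2 residual, the model's bias is -0.20 and the paired test's is -0.09.

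**Setting non-completers' change to zero.** Take 21 completers with mean change d and SD s, and add 9 zeros. The mean becomes 0.7d. For small d the SE becomes s x sqrt(20/29)/sqrt(30) = 0.1516s, so t = 4.62 d/s. The paired t is sqrt(21) x d/s = 4.58 d/s. The estimate shrinks but the test is the same: simulated error rates were 9.3% v 9.3% and 13.9% v 13.9%.

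**The case against.** The strongest case against acting is that these are exploratory outcomes in a 30-person pilot, no decision rule depends on them, and the bias is small beside the noise. At r = 0.5, 30% dropout and D = 0.48, a bias of 0.07 SD sits against an SE of about 0.22, and root mean squared error falls only from 0.231 to 0.215. That stands, and it limits the weight of the point. It does not remove it, because the change in rejection rate is not small and the better analysis needs no new data.

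Several stronger readings are tempting but unsupported:

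- **That the protocol forecasts high attrition here.** Section 1.0 describes a class of interventions and hopes that social features will improve retention.
- **That the change is biased whenever dropout depends on baseline.** The slope of T2 on T1 must also differ from 1.
- **That the model always removes the bias at almost no cost.** This requires dropout to depend only on observed values, and the SE can rise by about 30% when dropout is heavy and strongly driven by T1.
- **That Sections 11.0 and 17.0 promise withdrawn participants a place in the change test.** They are retention and withdrawal terms. They show that the T1 values will exist, not that this test must use them. Missing T2 is also broader than formal withdrawal.

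A mixed model does add nothing with one pre and one post value if it is fitted to completers, because it then returns the paired result. The gain comes from including participants who have T1 only. A plain maximum-likelihood fit with a normal reference rejected 6.3% to 6.8% at nominal 5%, so the small-sample method must be specified.

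**Conclusion.** The point holds in a limited form. As written, Section 22.0 gives a completers-only estimate of change with no stated missing-data assumption. If dropout depends on T1 and the T2-on-T1 slope is below 1, that estimate is off by about 0.04 to 0.17 SD at 30% to 40% dropout with a mild to moderate T1 link. A nominal 5% one-sided test then rejects in about 8% to 17% of null trials, or well below 5%, depending on who leaves. Every dropout rate, correlation, SD, mechanism and alpha behind these figures is an assumption. If retention is high or leavers resemble stayers at T1, the problem largely disappears.

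A reader might infer that the model would make the pilot's change interpretable as an intervention effect. It would not: with one arm, neither analysis separates the intervention from change over time or from regression to the mean in the whole sample. The primary measures in Section 22.0 are untouched by this point.

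**What to change.** In Section 22.0, for each preliminary outcome:

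1. Replace the paired t test with a REML repeated-measures model: time (T1, T2) as fixed effect, unstructured 2x2 covariance, small-sample degrees of freedom such as Kenward-Roger. Include every consented participant with a T1 value, whether or not T2 is present.
2. Report the mean change with a 95% confidence interval.
3. Keep the completers' paired analysis as a sensitivity analysis.
4. Add a delta-adjusted analysis that shifts non-completers' T2 over a range stated in advance. A shift moves the overall mean by the dropout fraction times the shift: at 30% dropout, 0.5 SD moves it by 0.15 SD. Do not use a zero-change analysis for this purpose, since it repeats the paired test.
5. Tabulate T1 values for completers and non-completers, so readers can see whether selective dropout occurred.

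The cost is SAP wording and a few lines of R, which the plan already names as its software; T1 is already collected and retained. The downside is an assumption that dropout depends only on observed values, which is why step 4 is needed. The SE changes from about 3% smaller to 4% larger at 30% dropout with a mild to moderate T1 link. It is up to about 8% larger at 40%, and about 30% larger if dropout is heavy and strongly driven by T1.
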